also be given a wireless weight scale to obtain weight measurements throughout the trial, at which point they will be randomized to either the adapted ABT intervention or an enhanced care group using a randomized block design. The ABT intervention for adolescents will be 6 months in duration. Participants randomized to the ABT intervention group will attend 15 remote intervention visits that are each 90 minutes in length. The sessions will be weekly for the first 2 months, bi-weekly for the next 2 months, and monthly for the last 2 months. Each session will be recorded. Participants randomized to the enhanced care group will receive a total of 15 emailed handouts on elements of a healthy lifestyle over the 6-month period and will participate in a midpoint one-on-one nutrition consultation with [name]. Handouts will be emailed at the time each of the ABT sessions occurs.

The study will be conducted remotely via Zoom. The randomized controlled trial will include intervention cohort sizes of ~7-10 adolescents with the target sample size of the study equal to 20 adolescents in each group (ABT intervention and enhanced care groups).

Data To Be Collected (what will be collected, where it will be stored, how it will be stored). For those who do not pass the screening, information collected will be destroyed immediately. For those who do pass the screening, a subject ID number will be assigned. Study data will be stored using REDCap behind the firewall at the University of Florida. Only designated members of the study team will have access to the study data. The database will contain personal identifiers including name, address, phone number, email address, birth date, and race/ethnicity.

Audio/visual recordings from the focus/writing groups and ABT intervention sessions will be transcribed, as necessary. Personal information will not be identified on the transcripts and confidentiality will be strictly maintained. Study data including audio/visual recordings and paper documents will be stored in locked filing cabinets. The subject ID assigned to each participant at the beginning of interaction will be that participant's assigned ID number for all study documents.

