Inclusion/Exclusion Criteria. We will limit our recruitment to adolescents ages 14-19 and OW/OB equal to or greater than the 85th percentile for sex and age as determined by CDC growth charts. Adolescents will be excluded if they have active cancer or cancer requiring treatment in the past 2 years, active or chronic infections (e.g., HIV or TB), active kidney disease, lung disease, known pregnancy or plans to become pregnant in the next 2 years, plans to move out of the area in the next year, a diagnosis of CVD or diabetes, autism, any intellectual disability (e.g., down syndrome), any condition prohibiting physical activity, an eating disorder or substance abuse disorder, having recently begun a course of or changed the dosage of any medications known to affect appetite or body composition, weight loss $\geq 5\%$ in the previous 6 months, or if they do not follow the study plan.

How Participants Will Be Recruited. Eligible participants will be identified at outpatient clinics such as Children's Medical Services, the Consent2Share program through IDR, and HealthStreet. Social media recruitment will also be conducted via the CTSI Recruitment Center. Based on study interest, the study team will notify potentially eligible persons about the research study and elicit feedback regarding their interest in participation. Once interest has been assessed and confirmed, the research team will reach out to these potential participants regarding the specific program requirements and will move forward with conduct of the screening and baseline visits to determine qualification to participate.

Randomization. Adolescent participants in the randomized controlled trial, stratified by sex, will be randomized by block randomization using random block sizes of four and eight for the ABT intervention portion of this project. Only the biostatistician on the project ([name]) will have access to the file of random assignments, created before the study. Cards will be created with the study ID numbers and the corresponding assignments and will be placed into sealed envelopes, which will be kept in a locked drawer. As successive patients are recruited and assigned their study ID, the envelope with the next chronological number

will be opened for assignment to one of the two groups. Randomization will occur after participants have completed all pre-treatment assessments and the personalized nutrition consultation.

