Blinding. Due to the nature of the intervention, it will not be possible to blind the instructor administering the intervention or participants. In all other aspects of the trial, we will employ blinding. Data managers, statisticians, and investigators drawing conclusions will be fully blinded. We will follow the rule that statistical analyses are conducted with the arms coded as 'intervention A' and 'intervention B'. The investigators will write two abstracts while blinding is intact; one assuming the ABT (experimental arm) is 'intervention A' and the enhanced care arm is 'intervention B', and one assuming the opposite. After this, the code will be broken by the data manager.

Data Analysis Plan. Qualitative outcomes data will be collected after each focus group to develop thematic saturation for adaptation of the adult ABT protocol for the OW/OB adolescent population.

Primary and secondary outcome data will be collected at 3 time points for the ABT pre-test (baseline, mid-treatment, and post-treatment).

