Primary and secondary outcome data will be collected at 2 time points for both the in-person ABT intervention and self-guided, at-home ABT intervention groups: baseline and post-treatment. We will begin with comparing descriptive statistics for baseline data between the two adolescent groups, followed by data from post-treatment. All data will be inspected for errors and inconsistencies across time points. For the feasibility and acceptability aim (Aim 2a), outcomes will be defined primarily by rates: recruitment, retention, and satisfaction will be calculated and compared between the groups. These rates will aid determination of overall feasibility of this intervention for a larger trial and will inform modifications to improve recruitment/retention of participants. While we will not be adequately powered to demonstrate efficacy, we will use analytic techniques similar to what would be done for a larger trial that did have sufficient statistical power (using an intention to treat approach). For the outcomes of change in BMI z-score and percent body fat (and other continuous measures), linear mixed models will be used to estimate and compare mean changes in BMI z-score between the groups, adjusting for baseline BMI z-score. Given the small sample size, the Kenward-Roger approximation for the denominator degrees of freedom will be utilized to ensure valid inference^[15]. Model selection of the covariance structure is minimized; and we will model directly the variance of the outcome at post-intervention. As this is a pilot study, SDs of these

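### Two separate, minor gaps in the main model: it omits the sex stratum, which makes intervals slightly too wide, and it makes no allowance for ABT cohort, which makes them too narrow if sessions are run in groups and outcomes correlate within them

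*Combined protocol and SAP*

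**What the plan says.** All references are to the combined protocol and SAP, Section 6, unless stated.

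- **Main model (Data Analysis Plan).** Linear mixed models will estimate and "compare mean changes in BMI z-score between the groups, adjusting for baseline BMI z-score". The sentence also covers percent body fat and other continuous measures, but BMI z-score is the only baseline it names. Kenward-Roger degrees of freedom are used because the sample is small, and the post-intervention variance is modelled directly.
- **Sex.** Under Randomization, participants, "stratified by sex, will be randomized by block randomization using random block sizes of four and eight". In the analysis, sex appears only among the covariates whose interactions with group and time are explored for effect modification. The trial name at the front of the file refers to adolescent girls.
- **Cohorts and delivery (Research Plan).** The trial has "intervention cohort sizes of ~7-10 adolescents with the target sample size of the study equal to 20 adolescents in each group". ABT consists of 15 remote 90-minute visits held over Zoom. By contrast, "the enhanced care group will receive a total of 15 emailed handouts", and its participants "will participate in a midpoint one-on-one nutrition consultation". On timing: "Handouts will be emailed at the time each of the ABT sessions occurs".
- **Blinding.** Analyses are run with the arms labelled A and B, and two abstracts are written before the code is broken.
- **Use of the results.** The plan says the trial is not powered for efficacy. Effect sizes are reported as a sign of potential efficacy but are barred from later power analyses.

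No ICC, design effect, cohort term or significance level appears in the documents.

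**The concern.** The two omissions act in opposite directions, so they need to be kept apart.

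**Sex.** Stratifying balances sex across the arms and so removes its contribution to the variance of the treatment difference. A model without sex leaves that contribution in the residual variance. The standard error is then overstated and the benefit of stratifying is lost.

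**Cohort.** If ABT participants attend together, those in the same cohort share an instructor, a peer group and a schedule, so their outcomes may correlate. Enhanced care has no such grouping. A model that treats all 20 ABT participants as independent then understates the variance of the ABT mean. Kenward-Roger does not help, because it works on the variance components that are in the model and cannot supply one that is absent. Modelling the post-intervention variance directly, even separately by arm, still treats participants as independent.

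What is at stake is how precise the ABT effect appears to be. Nothing in the plan tells a reader that the intervals assume no cohort effect.

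**Working it through.** **Inputs from the documents.** 20 per arm; ABT cohorts of about 7-10, so two cohorts of 10 or three of 7, 7 and 6; enhanced care delivered individually; stratification by sex. The 20 per arm comes with no derivation, so there is no figure of the plan's own to reproduce.

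**Assumptions.** Two-sided 5% test; ICC 0.01, 0.05 or 0.10; equal total variance in the arms; sex explaining 5% of outcome variance. The documents give none of these.

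**Sex omitted, no cohort effect.** Scale the outcome variance to 1 and take sex as half and half in each arm.
- True variance of the difference: 0.95 × 2/20.
- Variance that the model without sex estimates, on average: (0.95 + 0.05 × 20/19) × 2/20 = 1.0026 × 2/20.
- Ratio of true to naive SE: √(0.95/1.0026) = 0.973.
- Critical value 2.024 (38 df) divided by 0.973 is 2.080, giving a type I error of about 4.4%. Simulation gives 4.4-4.5%.
- In a simulated analysis adjusted for own baseline, mean interval width is 0.899 with sex and 0.923 without: 1 − 0.899/0.923 = 2.6% narrower with sex.

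**Cohort omitted, clustering in the ABT arm only.**
- Design effect for the ABT mean: DE = 1 + ICC × (Σm²/20 − 1).
- Two cohorts: Σm²/20 = 200/20 = 10, so DE = 1 + 9 × ICC.
- Three cohorts: Σm²/20 = (49 + 49 + 36)/20 = 6.7, so DE = 1 + 5.7 × ICC.
- Ratio of true to naive SE of the difference: √((DE + 1)/2).

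Type I error is from simulation (pooled t-test, 38 df):

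| Cohorts | ICC | DE | SE ratio | Type I error |
|---|---|---|---|---|
| 10, 10 | 0.01 | 1.09 | 1.02 | 5.5% |
| 10, 10 | 0.05 | 1.45 | 1.11 | 7.7% |
| 10, 10 | 0.10 | 1.90 | 1.20 | 10.5% |
| 7, 7, 6 | 0.01 | 1.057 | 1.01 | 5.3% |
| 7, 7, 6 | 0.05 | 1.285 | 1.07 | 6.7% |
| 7, 7, 6 | 0.10 | 1.57 | 1.13 | 8.5% |

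At ICC 0 the simulated error is 5.0%. At ICC 0.10 the effective ABT sample is 20/1.90 = 10.5 or 20/1.57 = 12.7.

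**Dropout.** With an assumed 15 per arm remaining, the errors at ICC 0.01, 0.05 and 0.10 are about 5.4%, 6.9% and 8.9% (cohorts of 8 and 7) and 5.2%, 6.2% and 7.4% (three of 5).

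**Both omitted, as the plan stands.** With 20 per arm: about 4.9%, 7.1% and 9.9% (two cohorts) and 4.7%, 6.1% and 7.8% (three).

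**Is a fixed-ICC interval sound?** Only if its ICC is true. With two cohorts, the 0.05 multiplier leaves 7.5% error when the true ICC is 0.10, and the 0.10 multiplier gives 2.0% when the true ICC is 0. Estimating the ICC is no alternative: at a true ICC of 0.05, 95% of estimates from two cohorts fall between −0.11 and 0.45, and 57% are at or below zero.

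**The case against.** **The premise is inferred.** The documents never say that trial sessions are held in groups. If they are individual, the cohort point falls. If a cohort is only a calendar wave shared by both arms, as the timing of the handouts could suggest, omitting it is mildly conservative: 4.3-4.9% in simulation. This stands, and the point has to remain conditional. Group delivery is still the natural reading: a cohort size has little purpose for individual sessions, and the plan marks only the dietitian contacts as individual.

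**It is an unpowered pilot.** No decision rule depends on these intervals, and the effect sizes will not feed a power calculation. This also stands and keeps both points minor.

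**Sex is already in the analysis.** It is, but as a possible effect modifier in exploratory work, not as a stratum adjustment in the main comparison.

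**Stronger readings to avoid.**
- A reader might infer that both omissions make the intervals too narrow. The sex omission does the reverse.
- A reader might infer that the trial's error rate is about 10%. That needs group delivery, an ICC of 0.10, two cohorts and no dropout, and the documents establish none of the first three and expect some dropout.
- A reader might infer that percent body fat and the other outcomes will be adjusted for baseline BMI z-score. The sentence is probably shorthand and needs only clearer wording.
- A reader might infer that allowing for cohort requires participant-level cohort data and breaking the A/B code. A fixed-ICC inflation needs only cohort sizes.

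**Conclusion.** Both points hold as minor improvements.

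**Sex.** The stratum is missing from the main model, and intervals are slightly too wide: about 4.4% error instead of 5% if sex explains 5% of variance. The point is moot if only girls are randomized, which the trial name suggests and the stratification contradicts.

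**Cohort.** For any positive within-cohort ICC under group delivery in the ABT arm alone, the naive standard error is too small. Over the assumed ICC range of 0.01 to 0.10 the true one is about 1% to 20% larger. Group format and ICC are both assumptions, and the type I errors shrink somewhat with dropout. The documented gap is that the plan states neither the session format nor that its intervals assume no cohort effect. This does not show that the planned analysis is invalid for a pilot's purposes.

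**What to change.** 1. **Main model.** State that each continuous post-treatment outcome is modelled on arm, that outcome's own baseline and sex. Naming the own baseline is a clarification of wording. Reconcile the trial name with the stratification by sex, and drop the sex term if only girls are randomized. Cost: wording and 1 degree of freedom.
2. **Session format.** State whether ABT sessions are delivered in groups.
3. **If they are,** say that the main intervals assume no cohort effect. Report sensitivity intervals with the ABT-arm variance multiplied by DE at fixed ICC 0.01, 0.05 and 0.10, and say that each is calibrated only if its ICC is true. Do not rely on an ICC estimated from two or three cohorts.
4. **Blinding.** Use the planned cohort sizes and inflate arm A and then arm B, in line with the two-abstract procedure. With 20 per arm and equal variances the multiplier is the same whichever arm is ABT. No participant-level cohort file is needed, and the work need not wait until the code is broken.

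The sensitivity intervals will be about 1-20% wider than the main ones. Adding sex also removes a small conservative offset to any cohort effect. In the simulated baseline-adjusted analysis with two cohorts, error rises from 7.0% to 7.7% at ICC 0.05 and from 9.8% to 10.6% at ICC 0.10. The sex term should therefore be paired with the cohort sensitivity intervals.

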The 6-month pre-test adolescent ABT intervention will include 90-minute sessions held weekly for 2 months, bi-weekly for 2 months, and monthly for 2 months, for a total of 15 sessions. Following each session, questions will be asked of the adolescents regarding the feasibility, process, and content of the adolescent ABT intervention. Beginning at week 2 of the intervention, weight check-ins will be conducted at each remaining session and feedback will be provided to the participants. Additionally, between sessions 14 and 15, members of the study team will contact participants to check in on their status and provide an opportunity for participants to informally discuss the program and/or ask questions the study team can address. The pre-test intervention will be completed with ~10-20 adolescents.

Adaptations to the randomized controlled trial (described below) are in response to COVID-19.

Once the ABT intervention has been modified following the pre-test, adolescent subjects will be recruited for the randomized controlled trial. Initially, this was planned to be an in-person trial, but we have adapted it to a remote intervention in response to COVID-19. Participants will complete pre-treatment and post-treatment assessments. Assessments conducted at each of these time points include surveys, weight measurements, dietary intake, and physical activity. Upon consent (and assent, as needed), participants will complete a series of questionnaires to assess demographic information, eating behaviors, self-regulation, self-image, quality of life, social support, depression, resilience, life experiences, stress levels, and taste/sensation. Dietary intake will also be assessed using 24-hour dietary recalls. Recalls will include 2 weekdays and 1 weekend day. Once participants have finished surveys and dietary recalls, they will participate in an individualized feedback session with [name], a registered dietitian. During this time, [name] will provide personalized feedback to the adolescent based on their 3-day dietary recalls. Participants will then be given an accelerometer and sleep log with instructions for use during a 7-day period and will then be asked to return the sleep log and accelerometer after the 7-day period is complete. They will

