Anthropometric and health-related data being collected at pre- and post-treatment of pre-test includes: height; weight; waist circumference; heart rate; blood pressure; percent body fat; urine sample; stool sample; metabolic blood panels; 3 24-hour dietary recalls; accelerometer data; and surveys/questionnaires. Mid-treatment data collection (in the pre-test intervention only) will be limited to anthropometrics (height, weight, waist circumference), blood pressure, heart rate, 3 24-hour dietary recalls, accelerometer data, and select questionnaires.

In the remote version of the randomized controlled trial in response to COVID-19, anthropometric and health-related data being collected at pre-treatment and post-treatment includes: height; weight; 3 24-hour dietary recalls; accelerometer data; and surveys/questionnaires.

The testing of biological samples collected for the study includes: blood, stool, and urine. Adolescents will be asked to collect stool and urine using a self-administered collection kit during or after the pre- and post-treatment visits. Self-administered collections performed at home (after the study visit) will be retrieved by the study team at no cost to participants. Blood draws will be completed by a certified phlebotomist during the clinic visits. Testing will be completed using Enzyme-Linked Immunosorbent Assay (ELISA).

Urine and stool samples may be stored for analysis in the Academic Research Building in the Department of Molecular Genetics and Microbiology, Room R1-156. Samples will be de-identified for processing and storage. Specimens in this lab are only available to authorized users. Urine and stool samples and data will only be released to the PI or PI-designated researchers with appropriate IRB approval. Blood samples may be stored in the UF Diabetes Institute as part of a bio-bank only available to authorized users. This bio-bank is the Diabetes Institute Study Bank (IRB201400703). Blood samples and data will only be released to the PI or PI-designated researchers with appropriate IRB approval.

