Precautions will be taken to minimize participant risk including: 1) participants will be told they can discontinue participation at any time or decline to answer any specific questions; 2) unique participant IDs will be utilized on all study documents; and 3) data will be kept confidential, stored on secure servers, identifiers will be destroyed when possible, and data access will be

limited to the study team. Individual information will not be released to anyone outside this project and will only be assessed by those actively working with the study team. If a participant indicates that he/she is going to hurt his/herself or someone else at any time throughout the study, a member of the study team will call '911' and the participant will be asked not to leave their home until first responders arrive. Additionally, we utilize the BDI-II as a screening tool for this study to identify suicidality. Answers to any question regarding suicidality are reviewed by study staff prior to the participant being randomized into either of the arms of the study. Should any participant indicate anything other than that they are non-suicidal, our team will refer the individual to the Crisis Hot Line and consult with co-investigator, [name], a licensed psychologist.

8. Possible Benefits:

There are minimal risks associated with this project and the benefits outweigh the risks. There may be immediate and direct benefits to some of the individuals who participate in this study. Through conduct of this research, we will be able to adapt and assess the effects of an ABT weight loss intervention in adolescents ages 14-19. This will assist in the development of future weight loss interventions for adolescents. Of direct benefit to the participants, some may be likely to lose weight and improve their cardiometabolic health profile.

9. Conflict of Interest:

There are no conflicts of interest to disclose.

References

1. Juonala , M., et al., *Childhood Adiposity, Adult Adiposity, and Cardiovascular Risk Factors*. New England Journal of Medicine, 2011. **365**(20): p. 1876-1885.
2. Ogden, C.L., et al., *Trends in obesity prevalence among children and adolescents in the united states, 1988-1994 through 2013-2014*. JAMA, 2016. **315**(21): p. 2292-2299.
3. Ogden, C.L., et al., *Prevalence of childhood and adult obesity in the United States, 2011-2012*. JAMA, 2014. **311**(8): p. 806-814.

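### The only deadline for reading suicidality answers is randomization, which falls at least 7 days after the baseline survey and never arrives for anyone who leaves first

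*Combined protocol and SAP*

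**What the plan says.** Section 7 (Possible Discomforts and Risks) states that "we utilize the BDI-II as a screening tool for this study to identify suicidality". It then gives the timing: "Answers to any question regarding suicidality are reviewed by study staff prior to the participant being randomized". Any answer short of clearly non-suicidal leads to a Crisis Hot Line referral and consultation with the psychologist co-investigator. A separate rule calls for 911 if a participant indicates intent to harm themselves or someone else. Neither rule says when a written answer must be read.

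Section 6 (Research Plan) sets the order of baseline steps in the randomized trial:

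- Surveys: "Upon consent (and assent, as needed), participants will complete a series of questionnaires to assess demographic information". The BDI-II is on the list of survey measures.
- Three 24-hour recalls (two weekdays, one weekend day), then a dietitian session once surveys and recalls are done.
- An accelerometer and sleep log, with participants "asked to return the sleep log and accelerometer after the 7-day period is complete".
- A scale and allocation: participants will "also be given a wireless weight scale to obtain weight measurements throughout the trial, at which point they will be randomized".

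Under Data To Be Collected, for the remote trial, "anthropometric and health-related data being collected at pre-treatment and post-treatment includes: height; weight; 3 24-hour dietary recalls; accelerometer data". Under Randomization, "Randomization will occur after participants have completed all pre-treatment assessments and the personalized nutrition consultation". The file contains the protocol twice, and these statements are the same in both copies.

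**The concern.** The reading of a safety screen is tied to a trial milestone, not to receipt of the answer. That milestone comes at the end of a baseline sequence lasting a week or more, and some participants never reach it.

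The participants are adolescents taking part from home, so the survey is not attached to a clinic visit where someone would look at it. Having chosen to ask about suicidality, the protocol names a sensible response. For a written answer, though, the referral, the psychologist consultation and the 911 rule all depend on someone having read the form. As written, full compliance is possible while a positive answer waits a week or longer. For a participant who drops out before randomization, it can wait indefinitely.

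The point is confined to the baseline survey of the randomized trial. It does not touch the estimand or the analysis.

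**Working it through.** The protocol gives no turnaround figure to reproduce, so the check is a timeline.

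**Inputs.** Deadline: before randomization (Section 7). Order of steps: surveys and recalls, then dietitian session, then 7-day wear (Section 6). Accelerometer data count as pre-treatment data (Data To Be Collected). Randomization follows all pre-treatment assessments and the consultation (Randomization).

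**Formula.** Days from survey to earliest randomization = (days from survey to last recall) + (wait for dietitian session and device start) + 7. The middle term is set to 0, which gives the shortest possible gap.

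**Lower bound.** If the survey is finished last, on the day of the dietitian session and device hand-out: 0 + 0 + 7 = 7 days.

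**Survey first, recalls on three separate days.** The table gives the earliest day of the last recall, counting the survey as day 0. The figure after adding 7 is in brackets.

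| Survey day | First recall same day | First recall next day | Next-working-day limit |
|---|---|---|---|
| Mon | 5 (12) | 5 (12) | 1 |
| Tue | 4 (11) | 4 (11) | 1 |
| Wed | 3 (10) | 3 (10) | 1 |
| Thu | 2 (9) | 4 (11) | 1 |
| Fri | 3 (10) | 4 (11) | 3 |
| Sat | 3 (10) | 3 (10) | 2 |
| Sun | 2 (9) | 6 (13) | 1 |

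For example, a Thursday survey with same-day recall uses Thursday, Friday and Saturday, so the last recall is day 2 and 2 + 7 = 9. A Sunday survey with the first recall on Monday must wait until the next Saturday for its weekend day, so the last recall is day 6 and 6 + 7 = 13. The ranges are 9-12 days (same-day start) and 10-13 days (next-day start). These are the earliest dates on which the deadline can fall. Scheduling and device return only add to them.

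**Looser reading.** If the scale sentence in Section 6 means allocation at hand-over, before the wear week, the 7 drops out. The gap becomes 2-5 or 3-6 days, or as little as 0 if the survey is finished last.

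**Leavers.** Section 7 lets participants stop at any time. For someone who submits the survey and stops before randomization, the event that sets the deadline does not occur, so no date can be computed on either reading.

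**The case against.** The strongest reply is that a latest permitted date is not a delay. Review by staff is mandatory, calling the BDI-II a screening tool suggests early reading, and nothing in the protocol shows staff waiting until randomization. Staff also contact participants for the recalls and the dietitian session. All of this stands, and the finding does not claim that answers will go unread. None of it, however, requires the form to have been read by any earlier date.

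Second, turnaround may be set in a working procedure outside the protocol. That cannot be excluded. But the protocol does not leave timing open: it states a rule, and the rule is the wrong one for this purpose.

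Third, the 7-day figure depends on which sentence governs. The scale sentence in Section 6 is ambiguous, but it follows the description of device return, and the Randomization paragraph is explicit, so the longer reading is the better one. The two texts should still be reconciled. The 9-13 day figures also rest on an order of surveys and recalls that the protocol does not strictly fix. Only the 7 days of wear is a stated number. Counting the hand-out day as the first wear day would end the period with day 6, and a return after completion would still fall around day 7.

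Finally, the scope could be wider. Post-treatment surveys and the pre-test participants, who are never randomized, also have no review date under this rule. The finding does not rely on them.

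**Conclusion.** The concern holds. The protocol's only time limit for reading suicidality answers is randomization. Under the explicit randomization rule this falls at least 7 days after the baseline survey, and 9 to 13 days after it if the survey comes first and the recalls are on separate days. The assumptions are no waiting between steps and accelerometer wear counted as a pre-treatment assessment, as the protocol lists it. On the looser reading of the scale sentence the gap is 0 to 6 days. The absence of any deadline for people who leave before randomization depends on none of these assumptions. This is a gap in a required safety step, not evidence of actual delay. It should be corrected.

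**What to change.** In Section 7, replace the randomization-based limit with a rule such as: study staff review suicidality answers on receipt, no later than the next working day, for every person who submits the form, whether or not that person is later randomized. Giving the BDI-II during a live call would serve as an alternative. Record each review as a dated log entry, and require that entry before the allocation envelope is opened. Leave the Crisis Hot Line referral and psychologist consultation as they are.

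The next-working-day limit is a proposed standard, not one taken from the protocol. It brings the wait to 1 day for forms sent Sunday to Thursday, 2 for Saturday and 3 for Friday, in a week without holidays. Weekend cover or live administration would close the remaining gap.

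The cost is one sentence and a log kept by staff who already do the review, for a trial targeting 20 + 20 = 40 participants. The burden is that forms must be checked as they arrive. No design, endpoint or analysis changes.
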